## 4. ZIKA-SYN: joint statistical analysis

The statistical analysis plans set out in this document are all specifically designed to allow for joint analysis alongside other datasets, both those generated by the other EU-funded ZIKA programs, ZIKA-Plan and ZIKAlliance, and those generated by other non-EU funded consortia such as the ZIP (ZIKA in Pregnancy) study. The joint analysis must of course be absolutely restricted to bona fide prospective vertical transmission studies, a definition of which can be found in Section 5.

As a necessary first step in the design of an SAP, we now state the *properties* that a statistical analysis must have to meet the requirement of a joint statistical analysis in this context. The SAP must be able to deliver unbiased estimates of the target parameters, regardless of:

- 1. Differences between studies in the maternal populations studied, for example symptomatic women only, as opposed to all women.
- 2. Differences between collaborating centers in VTR and risk of adverse clinical outcomes, including residual differences after key covariates are taken into account.
- 3. Differences within and between centers in the temporal scheduling of laboratory tests to identify maternal infection in pregnancy.
- 4. Differences between studies or centers, or changes over time, in the tests used to detect maternal infection in pregnancy, including differences in the combinations of tests, or in the type of tests.
- 5. Difference between studies, or between centers within studies, in test sensitivity, specificity and cross-reactivity.
- 6. Differences between centers in the availability of surveillance data.

It can be shown that the SAP outlined in the following pages has these properties.

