#### 7.4 Analysis of gestational age at maternal infection

We start with an analysis that assumes perfect test sensitivity and specificity. The gestational age at the onset of maternal infection is  $\pi_i(t)$ , t in weeks. Although the period of interest is between just before conception and delivery, ie the interval  $-2 \le t \le G_i$ ,  $\pi_i(t)$  is defined over a wider interval  $-2 - D \le t \le G_i + D$ , where D is the maximum duration of a test of persistence. This is because a first IgM+ test D weeks after delivery, or an IgM- test D+2 weeks before conception, both provide information about the probability of infection during pregnancy. Because there may be a finite probability that the maternal infection occurred before conception,  $\sum_{-2 \le t \le G_i} \pi_i(t)$  can take any value

between 0 and 1. Some special cases help clarify the concepts:

7.4.1 Onset of infection marked by symptoms. If a woman has symptoms in pregnancy starting at T then  $\pi_i(t) = 1$ , if t = T and  $\pi_i(t) = 0$ , if  $t \neq T$ .

7.4.2 Seroconversion alone. If the interval is defined by seroconversion during pregnancy, ie between a last lgG- at  $t_1$  and a first lgG+ at  $t_2$ , then in the absence of any other information,

$$\pi_i(t) = 1/(t_2 - t_1 + 1)$$
, if  $t_1 \le t \le t_2$ , else 0.

7.4.3 Surveillance data alone. Alternatively, suppose there are surveillance counts M(t) of suspected or confirmed cases (of ZIKV, DENV, or CHIKV) depending on the disease being studied [4], then the "a priori" distribution of when the infection might have occurred (given that it occurred in pregnancy) can be represented as a Dirichlet distribution:

$$\pi_i(t) = \alpha(t), \quad \alpha(t) \sim Dirichlet(M(t)), \quad -2 \le t \le G_i$$

7.4.4 PCR+ or IgM+, no surveillance data. If the specified interval is defined by a PCR+ or IgM+ test at time  $t_2$  and the earliest possible date of infection was  $t_1$  (which might be marked by an IgM- result, or  $t_1 = t_2 - D$ ) then, if the cumulative persistence distribution (the probability that persistence is d or less weeks) is  $F(d,\theta)$  with parameter(s)  $\theta$ , then (dropping the  $\theta$ ):

Author: [name] (UNIVBRIS)

20

$$\pi_i(t) = \frac{F(t_2 - t)}{\sum_{t_1 \le u \le t_2} F(u - t)}, \text{ if } -2 \le t \le t_2, \text{ else } 0$$

7.4.5 PCR+ or IgM+ with surveillance data. Now we assume the same test results, but surveillance data is available as well:

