The diagnostic algorithm will include confirmatory tests, and it is hoped that the effective specificity and sensitivity of the entire algorithm will be high. However, it may still be necessary to take false positives and negatives into account. Calculations capable of making these adjustments (see Appendix 2) assume that an estimate is available of the absolute a priori risk of infection, based on surveillance data. This is in contrast with the calculations in Section 7.4 which assumed perfect test accuracy, where only the relative probabilities were needed. The reason for this is that the probability that a ZIKV IgM+ is a false positive will be much higher if there is very little ZIKV circulating at the time, and much greater – depending on the cross-reactivity of the test – if there is a high incidence of DENV. Methods for obtaining information on the absolute incidence are explained in Section 8.1.7).

Note that adjustments for sensitivity and specificity need to be based on the properties of the entire algorithm, and on the entire set of results through the pregnancy.

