#### 8.1 Analyses to be carried out

Note that the estimates of incidence and seroprevalence that can be generated directly from ZIKA-VT are not true population estimates, because, within each collaborating center, the intention is to recruit pregnant women from areas at higher risk of arbovirus infection, and during periods of higher incidence. However, there is an interest in estimating incidence because it may correlate with risk of transmission or adverse clinical outcomes, if for example, both are related to viral load or degree of susceptibility.

All analyses will be initially stratified by center and mosquito season, or by center and year if there is no mosquito season. The text under each heading below should be understood as specifying one or more tables, in most cases separately for each of the three arboviruses.

8.1.1 Basic demographics of the sampled population. We will tabulate the numbers recruited each season, their age distribution. Further breakdowns will be by: socio-economic class, income range, type of housing, area of residence, residence stratified by arbovirus infection incidence (from surveillance data), as considered appropriate

8.1.2 Seroprevalence and cumulative incidence. For each arbovirus, the denominator for a seroprevalence estimate is the number of women who had at least one IgG test, and the numerator is the number who were IgG+ on their first test. In addition to "crude" (without adjustment) estimates of seroprevalence, we will obtain estimates of cumulative incidence  $\pi$ , which is (observed) seroprevalence p adjusted for IgG sensitivity and specificity, using the relationship

$$p = \pi Se + (1 - \pi)(1 - Sp)$$

Author: [name] (UNIVBRIS)

26

The sensitivity and specificity will be characterized as probability distributions based on the data available, assembled under the ZIKA-VID work package. The sources of this data will be continually updated (see *Appendix 4*).

If more than one test was used, results will be reported separately for each test (see Table 5)

The adjustment can be extended to account for cross-reactivity between DENV and ZIKV IgG tests, given information on sensitivity, general false positive rates, and cross-reactivity of both assays:

$$p_{Z} = \pi_{Z} S e_{Z} + (1 - \pi_{Z})(1 - S p_{Z}) + \pi_{D} X r_{Z}$$

$$p_{D} = \pi_{D} S e_{D} + (1 - \pi_{D})(1 - S p_{D}) + \pi_{Z} X r_{D}$$

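### Section 4 claims unbiased estimates whether or not a centre has surveillance data, but the timing rules printed for centres without it assume constant incidence

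*SAP*

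**What the plan says.** Section 4 sets the requirement: "The SAP must be able to deliver unbiased estimates of the target parameters, regardless of" six listed differences, of which the sixth is "Differences between centers in the availability of surveillance data". It then asserts: "It can be shown that the SAP outlined in the following pages has these properties". No demonstration follows.

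Section 7.4 gives the timing rules.
- 7.4.2 (seroconversion alone) spreads the onset uniformly between the last negative and first positive IgG, "in the absence of any other information".
- 7.4.4, headed "PCR+ or IgM+, no surveillance data", weights candidate weeks by the persistence function only.
- 7.4.5 is the same case with surveillance counts. Only there does the incidence term α(t) multiply the persistence term.

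On false positives, 7.6 says that the adjusting calculations "assume that an estimate is available of the absolute a priori risk of infection, based on surveillance data", and refers to 8.1.7. Section 5.1 is wider: the prior risk can come from surveillance and from information collected in ZIKA-VT. Sections 8.1.4 and 8.1.6 estimate incidence from the cohort's own tests, and 8.1.7 aligns those estimates with surveillance afterwards.

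Three other statements bear on the point. Section 7.5 says each woman faces a different incidence that varies over her pregnancy. Section 8.1 states the intention to "recruit pregnant women from areas at higher risk of arbovirus infection, and during periods of higher incidence". Section 1.3 says surveillance may tell more about timing than the tests do.

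**The concern.** Leaving α(t) out of the timing formula amounts to assuming that it is constant. The SAP says elsewhere that incidence is not constant, and it plans to recruit where and when it is high. A centre without surveillance data would therefore have its infections dated under an assumption that the plan itself rejects.

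VTR by gestational age is a main target, and ZIKA-SYN pooling relies on the six properties. The SAP also expects that VTR may differ between centres (2.1, 10.3). If the dating method depends on whether a centre has surveillance counts, part of an apparent centre difference could come from data availability.

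**Working it through.** The SAP gives no figure for this bias, so there is none to reproduce. Its one usable input is a mean IgM persistence of about 12 weeks (8.2.3). Everything else below is assumed. I weight by the probability of still being positive, 1 − F. The SAP prints F in 7.4.4 and 7.4.5, which is a separate matter; α(t) is missing from 7.4.4 either way.

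**1. One positive test, in closed form.** Assume perfect tests, exponential persistence with mean 12 weeks, a maximum duration of 52 weeks, and incidence proportional to exp(r·t). An onset k weeks before the test has weight exp(−c·k), with c = r + 1/12 and k = 0 to 52. The weight in k = a to b is proportional to exp(−c·a) − exp(−c·(b+1)).

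*First test, IgM+ at week 12.* Onset in weeks −2 to 12 is k = 0 to 14, all first trimester. Anything earlier is before the period of interest.
- Flat (r = 0): (1 − e^−1.25)/(1 − e^−4.417) = 0.7135/0.9879 = 0.722
- Rising (r = 0.1 per week): (1 − e^−2.75)/(1 − e^−9.717) = 0.9361/0.9999 = 0.936

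If incidence is rising and the true first-trimester VTR is 0.30, equation 7.1 gives an observed transmission share of 0.30 × 0.936 = 0.281. A flat prior explains that share with a VTR of 0.281/0.722 = 0.389.

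*First test, IgM+ at week 20.* First-trimester onset (weeks −2 to 13) is k = 7 to 22.
- Flat: (e^−0.583 − e^−1.917)/0.9879 = (0.5580 − 0.1471)/0.9879 = 0.416
- Rising: (e^−1.283 − e^−4.217)/0.9999 = (0.2771 − 0.0147)/0.9999 = 0.262

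Here the flat prior gives the first trimester too much weight. If later VTRs are lower, this pulls the first-trimester estimate down. The direction of the bias thus depends on when women are first tested.

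**2. Whole cohorts.** VTR by trimester was fitted through equation 7.1 to women dated by IgM alone, with perfect tests and a bell-shaped epidemic wave. The true first-trimester VTR is 0.30 throughout.

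| Assumed setting | Flat prior | Prior following incidence |
|---|---|---|
| Recruitment on the rise; visits at weeks 12/20/28/36 or 12/24/36; wave SD 6 or 10 weeks | 0.34 to 0.42 | 0.30 |
| Booking within 10 weeks of the peak; tests at 10/20/30; wave SD 5 | 0.38 to 0.40 | 0.28 to 0.35 (both SD 5 rows) |
| As above; tests at 18/30 | 0.17 to 0.22 | as above |
| Further large-sample fit, conceptions clustered around a wave | 0.22 to 0.44 | 0.30 |
| Conceptions spread evenly; visits at 12/20/28/36 or 12/24/36 | within 0.002 of 0.30 | 0.30 |

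The two SD 5 rows come from a simulation of about 40,000 to 48,000 women per scenario. Its comparator misses the truth by up to 0.05, so those rows are the least exact. That simulation put the bias under 0.02 for evenly spread conceptions with 10-weekly tests. With recruitment at or after the peak, a third-trimester VTR of 0.10 was estimated at 0.10 to 0.16.

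**3. The absolute risk.** Appendix 2 takes λ(t), the weekly incidence; the surveillance count M(t) does not appear in it. Sections 8.1.4 and 8.1.6 produce incidence without M(t). In 8.1.7, M(t) enters only after incidence has been estimated, to obtain the reporting fraction. The input therefore exists. What is missing is a statement that it replaces the surveillance-based risk named in 7.6 when a centre has no surveillance.

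**The case against.** Two stronger readings are tempting, and the document supports neither.

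- A reader might infer that the false-positive correction cannot run without surveillance, so that VTR would be diluted by the factors of 1.5 and 5 in the 7.6 example. It can run: Appendix 2 needs λ(t), and 5.1, 8.1.4 and 8.1.6 allow this to come from cohort data. Those factors describe a single uncorrected IgM test, whereas 7.6 provides for confirmatory tests and adjustment over the entire algorithm.
- A reader might infer that VTR by trimester is wrong in every centre without surveillance. The bias nearly vanishes when conceptions are spread evenly over the wave and visits are frequent. Symptom-dated women (7.4.1) do not depend on the prior. PCR, seroconversion and avidity narrow the interval for others, so calculations on IgM alone overstate the effect in a mixed cohort.

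It is also fair to say that 7.4 presents its cases as clarifying special cases under perfect accuracy, and that 7.5 recognises changing incidence as a reason to extend existing methods. But 7.4.4 is the only rule given for PCR+ or IgM+ women without surveillance, and allowing for test error does not restore the missing incidence term.

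Finally, no affected centre is identified. Appendix 7 so far names one source, which has weekly regional data. The harm is conditional and falls mainly on centres added later or pooled through ZIKA-SYN. Section 4 nevertheless makes its claim for exactly that situation.

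**Conclusion.** The point stands in a limited form. Property 6 is asserted without proof, and the printed rules for centres without surveillance do not have it, because they assume constant incidence against the SAP's own description. The bias in VTR by trimester ranges from practically none to material: a first-trimester 0.30 may be estimated at about 0.2 to 0.44 when recruitment clusters around a wave. Section 8.1 makes such clustering plausible but does not establish it.

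The size rests on assumed wave shapes, visit schedules, persistence distributions and true VTRs, with dating by IgM alone. The conclusion that the rules lack the claimed property does not rest on those figures. For the false-positive correction, the defect is a missing substitution rule.

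**What to change.** - Where surveillance data are absent, let the centre's own smoothed calendar-time incidence λ_c(u), estimated within the joint model from its test histories (8.1.4, 8.1.6), supply α(t) in 7.4.2 and 7.4.4.
- Use the same λ_c(u) as the absolute risk in Appendix 2, and amend 7.6 to agree with 5.1 that cohort data may provide it.
- Report the flat prior only as a sensitivity analysis.
- Restate property 6 in Section 4 as conditional on λ_c(u) being adequately estimated. The calculations above used a known incidence curve, not one estimated from sparse, interval-censored tests, so they do not show that the property would hold unconditionally after the change.

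The cost is one smoothed curve per centre in the model, and wider intervals in small centres. No additional data collection is needed.

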## 5. Background on vertical transmission rate

Vertical transmission rate can only be estimated from a prospective study. The defining feature of prospective vertical transmission studies is that ascertainment of maternal infection status must be independent of the infection status or clinical outcomes in the fetus, newborn, or child. This is most easily achieved if the mother's infection status is established before any examination of the fetus or newborn.

Author: [name] (UNIVBRIS)

14

Within that framework, the VTR is estimated by dividing the number of vertically infected children by the total number of women who were infected during pregnancy. However, there are difficulties in defining both the numerator and the denominator, due to the imperfect sensitivity and specificity of the diagnostic tests for ZIKV, CHIKV and DENV, and the imprecisely known gestational age at infection.

For this reason, a ZIKA-VT Diagnostic Expert Group (*Appendix 1*) will be responsible for keeping under review the best available information on: the sensitivity and specificity or all diagnostic tests (PCR, IgM, IgG); and the duration of PCR, IgM, and IgG responses following infection, and for advising on the interpretation of sequences of test results in the mother and offspring. The expert group will be responsible for determining the criteria for maternal infection, the timing of maternal infection, and vertical transmission.

#### 5.1 Denominator for VTR

Women will be classified as infected in pregnancy or not, based on PCR evidence of current infection, IgM evidence of recent infection, IgG evidence of seroconversion or rise in titer, assessed at several time-points during their pregnancy. Those infected in pregnancy form the denominator of the VTR.

To obtain unbiased estimates it may be necessary to take into account that IgM and IgG test are less than 100% sensitive and specific (see *Section 7.6*). There may also be miss-classification of the exposure due to serological cross-reactivity between ZIKV and DENV. Samples that are IgM+ for both are likely to be false positives on one of the two infections.

In order to take information on sensitivity, specificity and cross-reactivity into account in estimating vertical transmission rates and rates of congenital infection without bias, it is necessary to have information on the *a priori* risk of infection. This can be derived from surveillance data and information collected in ZIKA-VT (see *Section 8.1.7*).

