#### 2.1 Objectives relating to vertical transmission

There are two distinct questions relating to vertical transmission answered by the studies in ZIKA-VT and additional data from ZIKA-PED. The first concerns the risk of in utero transmission of ZIKV among

Author: [name] (UNIVBRIS)

11

infected mothers, while the second addresses the risk of adverse outcomes of maternal infection in the fetus, newborn and developing child.

In more detail, the objectives are therefore to estimate the role of gestational age (GA) at maternal infection (ZIKV, CHIKV, or DENV) and other risk factors in determining:

- (a) The vertical transmission rate (VTR)
- (b) Outcome of pregnancy following maternal infection: Fetal development, abnormalities on ultrasound, and outcomes of pregnancy (live-birth, stillbirth, miscarriage); GA at delivery; birthweight; anthropometrics including small for GA; cranial disproportion, and
- (c) Pediatric outcomes following maternal infection: Frequency, type, and severity of adverse outcomes (for example: growth, neurological, neurodevelopmental, ophthalmological, and auditory outcomes) up to 2-4 years of age:

In addition, the impact of maternal infection on both outcomes of pregnancy and pediatric outcomes must be studied: (i) in the presence of *in utero* transmission, (ii) in the absence of *in utero* transmission

The key risk factors of scientific interest for VTR, and for type and severity of pregnancy and pediatric outcomes, are: occurrence of maternal symptoms such as rash; co-infection with other arboviruses during pregnancy; previous infection with the same or different arboviruses, other co-infections. We will also recognize the possibility that VTR and risk of severe outcomes may vary between the collaborating centers, even when these risk factors are taken into account. Variables reflecting socioeconomic class or level of education will be treated as potential confounding variables as they may be correlated with both outcomes and exposure to ZIKV.

The same analysis plan will be applied to ZIKV, CHIKV and DENV.

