## 7.6 Accounting for imperfect test sensitivity and specificity, and cross-reactivity

As noted earlier, we need to calculate for each woman recruited into ZIKA-VT, the probability that she was infected in pregnancy, and the distribution of GA when this infection occurred, if it occurred at all, based on tests with imperfect accuracy.

Author: [name] (UNIVBRIS)

24

For example, a sequence of four ZIKV IgM- results throughout pregnancy, assuming there were no IgG, PCR tests and no symptoms, would be scored as "No evidence of maternal infection in pregnancy" in basic analyses, but there is a possibility that they are all false -ves.

As long as the testing algorithm is relatively sensitive, say 95% or more, the bias in estimates of the vertical transmission due to false -ves is likely to be negligible. A small proportion (<5%) of maternal infections would be missed from the denominator, but their babies will not be followed up, and so would also be missed from the numerator. The exception to this would be if they are not only congenitally infected but their congenital infection is apparent. But it can be shown that, on current evidence, this would lead to only a very slight over-estimation of the VTR.

The difficulties posed by false *positive* IgM tests are, however, far more serious. If the specificity of an IgM test is 95%, then 5% of uninfected mothers will receive false +ve results, and will be considered infected in pregnancy. If 10% of women are infected in pregnancy, then, for every 15 women considered as infected in pregnancy, only (approximately) 10 would be truly infected, and the vertical infection rate will be underestimated by a factor of 1.5. If incidence is lower, and only 1% of women are infected in pregnancy, then only 1 in 5 women being followed are truly infected and the vertical transmission rate will be underestimated by a factor of 5.

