8.1.6 Incidence of primary infections estimated by increase in seroprevalence. If we know or can estimate the cumulative incidence at a starting point T, then cumulative incidence at time t is related to incidence between t and T as follows:

$$\pi(t) = \pi(T) + (1 - \pi(T) \left( 1 - \exp\left( -\sum_{T \le u \le t} \lambda(u) \right) \right)$$

This can be modelled, for example assuming piece-wise constant incidence.

For DENV infection, which has been present for much longer, it may be preferable to model age-and time-specific cumulative incidence:

$$\pi(a,t) = \pi(a,T) + (1-\pi(a,T)\left(1-\exp\left(-\sum_{T \le u \le t} \lambda(a-T+u,u)\right)\right)$$

Using data from pregnant women, we would model incidence from time T and age 16 upwards.

These calculations assume that cumulative incidence can be estimated by adjusting seroprevalence for sensitivity and specificity as shown in *Section 8.1.2* 

8.1.7 Alignment with surveillance data: population estimates of incidence. Once estimates of incidence are available, they can be aligned with surveillance reports to estimate the proportion of incident infections (symptomatic or not) that are reported to the surveillance system. "Alignment" should be interpreted as putting the dates of the tests on the real timescale, so that incidence estimates for ZIKV, DENV, and CHIKV based on ZIKA-VT data can be compared to numbers of cases notified to national or regional surveillance centers, both confirmed and suspected.

If the estimated incidence in some period t is  $\lambda(t)$  and M(t) cases are reported in, say, the population of adult women aged 16-44, over the same time period and from the same area where ZIKA-VT is recruiting, then we can calculate the proportion of all infections that were reported over that time period as :

$$\theta(t) = \frac{M(t)}{N(1 - e^{-\lambda(t)})}$$

Where N is the relevant population size. This quantity can be examined over time to see if it remains relatively stable, and can be used in analyses of test persistence and adjustments for sensitivity and specificity needed to estimate the gestational age of maternal infection and vertical transmission rate (see Sections 5,7).

Further, once an estimate  $\theta(t)$  is available, it can be used to "gross-up" counts M(t), to estimate the true number of infections on a national or regional basis:  $M(t)/\theta(t)$ .

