#### A2.1 A single ZIKV IgM+ DENV IgM- test

To illustrate, we explore the implications of potentially false positive ZIKV IgM tests which cannot be attributed to DENV. To simplify we assume the DENV IgM is perfectly sensitive so that the -ve result rules out a DENV infection.

We assume a single ZIKV IgM+ DENV- test at week 20, and ask: what is the probability there has been a true maternal infection between weeks -2 and week 20, given a Z+D- IgM result at week 20? This quantity can be written as  $p(I_{Z,-2:20} \mid Z+D-_{20})$ . Let  $p(\overline{I}_{Z,-2:20})$  be the probability of no ZIKV infection between weeks -2 and 20. Using Bayes Rule, we expand the formula in section 7.4.5 to allow for imperfect test accuracy:

44

Author: [name] (UNIVBRIS)

$$\begin{split} p\Big(I_{Z,-2:20} \mid Z + D -_{20}\Big) &= \frac{p\Big(Z + D -_{20} \mid I_{Z,-2:20}\Big).p\Big(I_{Z,-2:20}\Big)}{p\Big(Z + D -_{20} \mid I_{Z,-2:20}\Big).p\Big(I_{Z,-2:20}\Big) + p\Big(Z + D -_{20} \mid \overline{I}_{Z,-2:20}\Big).p\Big(\overline{I}_{Z,-2:20}\Big)} \\ &= \frac{\displaystyle\sum_{-2 \leq u \leq 20} F(22 - u).Se\bigg(1 - e^{-\sum_{-2 \leq u \leq 20} \lambda(u)}\bigg)}{\displaystyle\sum_{-2 \leq u \leq 20} F(22 - u).Se\bigg(1 - e^{-\sum_{-2 \leq u \leq 20} \lambda(u)}\bigg) + (1 - Sp).e^{-\sum_{-2 \leq u \leq 20} \lambda(u)}} \end{split}$$

To calculate  $\pi_i(t)$  in this case, we have two components: one for the period up to the IgM+ result, the other after it:

$$\pi_{i}(t) = \begin{cases} \frac{\sum_{-2 \le u \le 20} F(22 - u).Se\left(1 - e^{-\sum_{-2 \le u \le 20} \lambda(u)}\right)}{\sum_{-2 \le u \le 20} F(22 - u).Se\left(1 - e^{-\sum_{-2 \le u \le 20} \lambda(u)}\right) + (1 - Sp).e^{-\sum_{-2 \le u \le 20} \lambda(u)}} & -2 \le t \le 20 \\ 1 - e^{-\lambda t} & 21 \le t \le G_{i} \end{cases}$$

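### The false-positive adjustment takes no account of the woman's symptoms, so it biases VTR in asymptomatic IgM+ women and can create a false symptom effect

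*SAP*

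**What the plan says.** Section 5.1 states that unbiased estimation with imperfect tests needs an a priori risk of infection: "This can be derived from surveillance data and information collected in ZIKA-VT". It refers to Section 8.1.7, which aligns ZIKA-VT incidence with surveillance reports "to estimate the proportion of incident infections (symptomatic or not) that are reported to the surveillance system". The resulting incidence therefore covers all infections together. Section 5.4 lets the risk vary with calendar time and circulating virus, and Section 7.6 makes it an input to Appendix 2.

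A2.1 then asks, for a woman who is ZIKV IgM+ and DENV IgM− at week 20, "what is the probability there has been a true maternal infection between weeks -2 and week 20". Its formula contains the persistence distribution F, Se, Sp and the prior 1 − exp(−Σλ(u)). It has no symptom term in either the prior or the likelihood.

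Symptoms are used elsewhere: as an onset date (5.3, 7.4.1), as a persistence covariate (7.5.2), as a stratifier in Tables 1, 3 and 4, and as the first-listed key risk factor for VTR, "occurrence of maternal symptoms such as rash" (2.1). Section 8.1.3 estimates the symptomatic proportion but does not pass it to the prior. Section 4 requires, and says it can be shown, that estimates are unbiased regardless of "Differences between studies in the maternal populations studied, for example symptomatic women only, as opposed to all women".

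**The concern.** Symptom status is itself evidence about infection. Suppose a share s of infected women and a share b of uninfected women have qualifying symptoms, with s > b. A woman without symptoms is then less likely to be infected than the average woman in the same place and week, and a woman with symptoms is more likely to be. A prior that leaves this out gives both the average.

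False positives are then concentrated among IgM+ women without symptoms, and the model does not know it. Section 7.1 multiplies V(t) by an infection probability that is too high for these women, so V is estimated too low for them. Entering symptoms in the βX term does not repair this: β absorbs the misclassification and reports it as a symptom effect.

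At stake are VTR, one of the two outcomes that Section 10.4 calls fundamental, its first-listed risk factor, and the pooling in ZIKA-SYN of symptomatic-only with all-women studies.

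**Working it through.** **The SAP's own figures.** Section 7.6: "If the specificity of an IgM test is 95%, then 5% of uninfected mothers will receive false +ve results". With Se = 1 and 10% infected, each 100 women give 10 true and 0.05 × 90 = 4.5 false positives. That is 14.5 flagged per 10 true, a factor of 1.45, in line with "for every 15 women considered as infected in pregnancy, only (approximately) 10 would be truly infected". At 1% the SAP says "only 1% of women are infected in pregnancy, then only 1 in 5 women being followed are truly infected" and gives a factor of 5. Its inputs give 1 + 0.05 × 99 = 5.95 flagged per true case, so about 6; the stated 5 matches the ratio of false to true positives (4.95). The symptom point does not depend on this slip.

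**Inputs.** From Section 7.6: Sp = 95% as an example, and q (probability of infection in the window) = 10% or 1%. Assumed, because the SAP gives no values: Se = 95%, with the persistence term F absorbed into it; s = 20% or 50%; b = 0 to 10%. True VTR is taken as equal with and without symptoms, and children of false-positive mothers as not vertically infected.

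**Formulas.**
- Credited by the plan: P0 = Se·q / [Se·q + (1−Sp)(1−q)]
- Correct, no symptoms: PA = Se·q(1−s) / [Se·q(1−s) + (1−Sp)(1−q)(1−b)]
- Correct, symptoms: PS = Se·q·s / [Se·q·s + (1−Sp)(1−q)b]
- Observed transmission in a stratum is V × (correct P) and the model fits V̂ × P0, so V̂/V = (correct P)/P0.

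**Asymptomatic women, b = 0, Sp = 95%.**

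| q | s | P0 | PA | V̂/V |
|---|---|---|---|---|
| 10% | 20% | 0.095/0.140 = 0.68 | 0.076/0.121 = 0.63 | 0.93 |
| 10% | 50% | 0.68 | 0.0475/0.0925 = 0.51 | 0.76 |
| 1% | 20% | 0.0095/0.059 = 0.16 | 0.0076/0.0571 = 0.13 | 0.83 |
| 1% | 50% | 0.16 | 0.00475/0.05425 = 0.09 | 0.54 |

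**Dependence on specificity** (same formulas, b = 0; V̂/V at s = 20% and 50%). At Sp 99%: 0.98 and 0.92 (q = 10%), 0.89 and 0.66 (q = 1%). At Sp 99.9%: 0.998 and 0.99 (q = 10%), 0.98 and 0.91 (q = 1%). If Sp = 100% or s = b, there is no bias.

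**Apparent symptom effect when the true ratio is 1, Sp = 95%.**

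(a) The Appendix 2 formula is used for both groups. P0 cancels and the ratio is PS/PA. With b = 5%:
- q = 10%: 0.894/0.640 = 1.4 (s = 20%) and 0.955/0.526 = 1.8 (s = 50%).
- q = 1%: 0.434/0.139 = 3.1 and 0.657/0.0917 = 7.2.

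(b) Symptomatic women are instead given π = 1, as in 7.4.1. The ratio is PS/(PA/P0). With q = 10% and s = 20%: 1/0.926 = 1.08 (b = 0), 0.955/0.933 = 1.02 (b = 2%), 0.894/0.943 = 0.95 (b = 5%), 0.809/0.961 = 0.84 (b = 10%). The sign changes with b.

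**The case against.** The strongest reply is that Appendix 2 is an illustration. It says that it simplifies, it treats one IgM result, and A2.3 leaves test sequences and the accuracy of the whole algorithm to be determined. Section 1.2 warns that parts of the SAP are generic. Symptoms are also not forgotten: Section 5.4 gives the expert group rules that combine tests with clinical findings, 7.4.1 uses symptoms to fix onset, and the false-negative example in 7.6 specifies a woman without symptoms.

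Much of this stands. A reader might infer that the SAP has decided to ignore symptoms, or that it gives every woman one population-wide prior. The documents support neither: the risk varies by week, area and virus, the Section 5.1 sentence does not exclude symptom data, and the framework is openly unfinished. What remains is that each place describing the prior omits symptom status. The expert rules are unwritten and yield confirmed, definite or possible labels, not a prior; 7.4.1 assumes perfect tests and leaves the asymptomatic bias untouched. A2.3 leaves open how sequences are handled, not where the prior comes from.

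The second reply concerns size. The 95% specificity is a hypothetical for a lone IgM test. Section 7.6 plans confirmatory tests, Section 7.5.3 provides PCR on all IgM+ women, and PCR is taken as effectively 100% specific (5.4), so PCR+ women escape the problem. This also stands, but Section 7.6 only hopes for high overall accuracy and accepts that adjustment may still be needed. Finally, Section 7.1 updates V(t) and π together, so the ratio V̂/V above approximates the effect and is not the planned estimator's output. The joint model has no symptom term in the infection probability either, so nothing in it is designed to remove the bias.

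**Conclusion.** The point holds for the adjustment as written, applied to IgM+ women without PCR confirmation. In asymptomatic women VTR is biased down whenever s > b and the algorithm's specificity is below 100%. On the stated assumptions the multiplier is 0.93–0.76 at 10% infected and 0.83–0.54 at 1%. These are illustrations: the SAP gives neither s, b nor the specificity of the full algorithm. With high overall specificity the bias is small, except at low incidence.

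A reader might infer that maternal symptoms will necessarily appear to raise VTR, or that ratios of 3 to 7 are to be expected. The documents do not support that. A falsely positive effect follows if the same formula is used for both groups, because symptomatic women are then under-credited and their VTR is biased up. If they are given π = 1, the sign depends on b, and the SAP does not say which treatment applies. Under either treatment an artefact generally remains when specificity is imperfect.

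Section 4 property 1 therefore does not hold for this adjustment as written: in a symptomatic-only study, using the unconditioned prior would understate every woman's risk.

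**What to change.** In Section 7.6 and Appendix 2, and in the extension to test sequences left open in A2.3, condition on symptom status. λ(t) is a weekly rate, so first form q = 1 − exp(−Σλ(u)) over the candidate weeks. Then use as prior odds:

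- no qualifying symptoms: q(1−s) / [(1−q)(1−b)]
- qualifying symptoms: q·s / [(1−q)·b]

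Equivalently, put symptoms in the likelihood. Estimate s (from the 8.1.3 data) and b inside the joint Bayesian model with infection status treated as uncertain, because both would otherwise be computed from the same error-prone classification. Add a sensitivity range for both. State which treatment applies to symptomatic IgM+ women without PCR confirmation, the adjusted probability or the fixed onset of 7.4.1. In ZIKA-SYN use the symptomatic form for symptomatic-only studies, and say in Section 4 that property 1 depends on this.

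The cost is SAP wording, two extra parameters and somewhat wider VTR intervals; how much wider cannot be worked out from the document.
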